**Spirometry Testing**

Each subject will undergo baseline spirometry assessment to determine eligibility. All subjects will perform baseline pre and post bronchodilator spirometry at Visit1 . Subjects will be asked to hold their bronchodilator (albuterol) for 2 hours prior to the PFT test.

**Subjects who meet the PFT criteria at Visit 1 will be required to be tested for COVID-19 prior to undergo the MCC measurements at Visits 2 and 3. The COVID testing will be done at the CTRC Montefiore Hospital by a trained nurse. The COVID testing is a safety measure requested by the PI to make sure staff present during the MCC measurements will not be placed at risk of contracting the virus during the study procedures. Subjects found ineligible per the PFT results, will be considered a screen fail and will not be tested.**

**Only patients with COVID testing negative will be invited to complete study visits 2 and 3.**

### **Study Questionnaires**

All subjects will complete the following self-administered questionnaires at Visit 1:

- 1) St. George's Respiratory Questionnaire (SGRQ)
- 2) COPD Assessment Test (CAT)
- 3) Modified Medical Research Council Dyspnea Scale (mMRC)
- 4) Exacerbation history

### **Schedule of Assessments**

#### **Visit schedule**

	Visit 1	Visit 2	Visit 3
Baseline MCC*		X	
Treatment MCC*			X
Questionnaires	X		
Pre and Post Bronchodilator Spirometry	X		

\* Baseline and Treatment MCC are randomized.

The Fisher and Paykel myAirvo2 heater/humidifier and Optiflow nasal cannula are commercially available devices that are used together to deliver heated humidified air or oxygen for breathing. The purpose of this study is to determine whether 4 hours of use of this device will improve mucus clearance in patients with chronic bronchitis. This may occur through hydration of airway secretions and possibly through splinting of the airways. Twelve subjects will be enrolled and perform two imaging days and a possible screening day. The primary outcome measure is mucociliary clearance as measured using a nuclear medicine imaging technique.

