**Study procedures:**

**MCC assessment**

- 1) Subjects will perform 2 MCC assessment study days. One to measure baseline MCC and the other to measure MCC during treatment with the cannula. Study days will be separated by 4-7 days. The order of the days will be randomized. Subjects will refrain from SABA use for 6 hours and LABA/LAMA use for 24 hours prior to Visits 2 and 3.
- 2) Subjects will arrive in nuclear medicine. They will lie recumbent in the nuclear medicine camera while background images are collected. They will then perform a Cobalt-57 transmission scan which allows for visualization of the lung outlines. Both scans are utilized during image analysis.
- 3) Subjects will be seated for the inhalation of the radiolabeled particles. 4 mCi of Technetium 99m sulfur colloid (Tc-SC) in 2ml of saline will be added to a DeVilbiss 646 Nebulizer driven by a DeVilbiss 8650D compressor and attached to a Spira Dosimeter. Using standardized procedures developed the Cystic Fibrosis Foundation (1), we will deliver the aerosol for 5 approximately minutes using a specified breathing pattern (30 breaths/minute) using inhalation flowrates of ~0.5 L/s.
- 4) Subjects will then return to the camera and lie recumbent while serial two-minute gamma camera images are collected for 90 minutes. On the intervention day, the nasal cannula will be applied after 5 images are collected. On the baseline day there will be no intervention. Coughs will be manually logged by study personnel.
- 5) After 90 minutes the subjects will exit the camera and remain in the waiting areas around radiology. They will continue inhaling from the cannula on the intervention day. Subjects will perform a 10 minute follow up image at t=4 hours and 10 minutes after the start of the imaging sequence. The 10 minute image may be delayed for several minutes if the gamma camera is in use at the specified time Subjects would resume their normal medications.
- 6) We will plot normalized retention vs. time and compare the percentage of deposited material cleared at t=90 min and up to 6 hours on the intervention days. Areas above the curve 90 min clearance curve will also be compared. We will calculate the central deposition percentage of the Tc-SC aerosol to ensure that Tc-SC aerosol delivery was similar on both testing days.

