- 7) Previous measurements from our group demonstrated a standard deviation of the intrasubject differences in MCC measurements ( $\sigma$ ) = 7.7% (2). Assuming  $\alpha=0.05$ ,  $\beta=0.2$ , and  $n=12$  matched pairs, we could detect a 6.8% (absolute) change in MCC rates via paired t-test. Average MCC rates in control subjects over 90 minutes have been reported to be 28.2% (1). MCC rate differences reported by Hasani et al were approximately 8% after 7 days of daily therapy (3).
- 8) We will replace subjects who do not complete both testing days until we have a total of 12 subjects with completed studies.

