Study of Humidified Air to Improve Mucociliary Clearance (MCC) in COPD:

NCT03935932

[name]., [name].
Pulmonary, Allergy and Critical Care Medicine
University of Pittsburgh

June 5, 2023

Statistical Analysis Plan:

We will plot normalized retention vs. time and compare the percentage of deposited material cleared at $t=90$ min and up to 6 hours on the intervention days. Areas above the curve 90 min clearance curve will also be compared. We will calculate the central deposition percentage of the Tc-SC aerosol to ensure that Tc-SC aerosol delivery was similar on both testing days.

Statistical comparisons will be made using paired non-parametric statistics to compare the baseline clearance day to the Airvo clearance day (Wilcoxon Signed Rank).

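### The primary outcome is named only as mucociliary clearance: two or three readouts are compared, and none is designated primary, ordered or adjusted for

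*Protocol*

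**What the plan says.** - **Primary outcome.** The Protocol's closing summary, under Visit schedule, says "The primary outcome measure is mucociliary clearance as measured using a nuclear medicine imaging technique". No other statement in either document designates a primary.
- **Readouts.** Item 6 of the Protocol's MCC assessment, repeated in the SAP, will "compare the percentage of deposited material cleared at t=90 min and up to 6 hours on the intervention days". The SAP adds: "Areas above the curve 90 min clearance curve will also be compared".
- **Test.** The SAP assigns the Wilcoxon signed-rank test to the comparison of the baseline day with the Airvo day. It does not list the readouts to be tested, and it gives no alpha, sidedness, order or multiplicity rule.
- **Imaging times.** Serial two-minute images run for 90 min (item 4). "On the intervention day, the nasal cannula will be applied after 5 images are collected". After that there is one late image (item 5): "Subjects will perform a 10 minute follow up image at t=4 hours and 10 minutes after the start of the imaging sequence".
- **Sizing.** Item 7 says that with 12 pairs and an SD of 7.7% "we could detect a 6.8% (absolute) change in MCC rates via paired t-test", with no time attached. The next sentence gives background: "Average MCC rates in control subjects over 90 minutes have been reported to be 28.2" percent.
- **Purpose.** The closing summary says the study is to "determine whether 4 hours of use of this device will improve mucus clearance".

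**The concern.** The readouts answer different questions. Clearance at 90 min describes a little over an hour of humidification, the late image describes the full session, and the area reflects how early clearance occurs within the first 90 min. They can disagree. With 12 subjects and no designation, a reader of a positive report could not tell whether the readout put forward was chosen beforehand or because it was the one that reached significance. If any one of several could count, the chance of a false favourable finding would also exceed that of a single test.

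**Working it through.** **1. Does the text fix the primary?**

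| Place | What it suggests | Designates a primary? |
|---|---|---|
| Protocol, Hypothesis | Improvement in real time, which fits serial 90-min imaging | No |
| Protocol, MCC assessment item 6, and SAP | 90 min is listed first; the areas are an addition | No |
| Protocol, MCC assessment item 7 | 90 min is the only time mentioned, but in a background sentence | No |
| Protocol, Visit schedule | Clearance, with no measure or time | Names the construct only |

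**2. Exposure behind each readout** (ignoring any gap between images)

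- Cannula applied after 5 × 2 = 10 min.
- At 90 min: 90 − 10 = 80 min of humidification.
- At the late image: 250 − 10 = 240 min, which is the 4-hour session.

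**3. The plan's own figure.** Inputs from item 7: SD 7.7%, n = 12, alpha 0.05, power 80%. Solve for δ such that a noncentral t on 11 df, with noncentrality δ√12/7.7, exceeds the two-sided critical value with probability 0.80. This gives δ = 6.84%, and power at 6.8% is 79.5%, so the stated 6.8% reproduces. One-sided gives 5.90%, so two-sided 0.05 is used below. The ratio 6.84/7.7 = 0.889 converts any other SD into a detectable change.

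**4. Size of one signed-rank test, n = 12.** Of the 2¹² = 4,096 sign patterns, 87 give a rank sum of 13 or less: 87/4,096 = 2.12% per direction, 4.25% two-sided. A cut-off of 14 would give 5.22%, which is too large. So a single test has a 2.1% false favourable rate (2.5% nominal).

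**5. Illustration: any one readout counts.** Paired differences were simulated under the null as multivariate Normal with equal correlation, 1,000,000 trials per case. A separate run of 400,000 per case agreed to within about 0.1 percentage point. The correlations are assumptions.

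| Readouts | Correlation | Favourable | Either direction |
|---|---|---|---|
| 2 | 0.95 | 2.9% | 5.8% |
| 2 | 0.8 | 3.5% | 7.0% |
| 2 | 0.5 | 4.0% | 7.9% |
| 3 | 0.95 | 3.4% | 6.8% |
| 3 | 0.8 | 4.5% | 9.0% |
| 3 | 0.5 | 5.6% | 11.1% |

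Unequal correlations may be more realistic, with the two 90-min readouts close and the late one less so. In the order 90 min-area, 90 min-late, area-late:

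- (0.95, 0.8, 0.75) gives 4.2% favourable.
- (0.9, 0.6, 0.6) gives 4.7%.
- (0.8, 0.5, 0.5) gives 5.2%.

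Independence would give 1 − (1 − 0.0212)³ = 6.2%. Percentage cleared at 90 min and the area above the same curve cannot be independent, so 6.2% is a bound that cannot be reached.

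**6. Two readouts or three?** The wording of item 6 attaches the late readout to the intervention days, so it may not be a paired comparison with baseline. On that reading only the two 90-min readouts are tested, and the two-readout rows apply.

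**The case against.** The strongest reply is that 90 min is plainly meant. It comes first, the areas are an extra, the sizing paragraph mentions only 90 min, and the hypothesis is about real-time change. Much of this stands: the text does lean to 90 min, and if that is the sole primary there is no inflation. But the sentence that declares the primary gives no time, and the detectable change is stated for clearance rates in general. A lean that a reader must assemble from several places does not prevent a later choice.

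Two stronger readings are tempting, and the documents do not support them.

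- **That the purpose sentence makes the 4-hour image the intended primary.** Its 4 hours describe how long the device is used, matching the Intervention section; they do not set a measurement time. What remains is that a 90-min readout covers only about 80 min of that use.
- **That the trial's false-positive rate is inflated, to as much as 6.2%.** The documents state no success rule and no correlations, and do not say that three signed-rank tests will be run. The 6.2% also needs an independence that two summaries of one curve cannot have.

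It is also fair to say that formal testing of secondary readouts is optional in a 12-subject physiological crossover; estimates with intervals are enough.

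**Conclusion.** The point holds as a gap in specification. The primary is a construct with two or three candidate readouts and no designation, order or adjustment. This rests on the text alone. The late readout has a separate inconsistency: analysis up to 6 hours against a single late image at 4 h 10 min, with its comparator unclear.

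The error rates are illustrative. They assume that any one readout significant at two-sided 0.05 counts, and they use correlations the documents do not give. On those terms the favourable rate is 1.4 to 1.9 times the exact single-test size for two readouts (2.9/2.12 to 4.0/2.12) and 1.6 to 2.6 times for three (3.4/2.12 to 5.6/2.12). Against the nominal 2.5% the ratios are 1.2 to 1.6 and 1.4 to 2.2. Two-sidedness is inferred from reproducing the 6.8%. This should be corrected. It does not invalidate the design.

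**What to change.** Before analysis, in both Protocol and SAP:

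1. Name percentage cleared at 90 min, baseline day against Airvo day, signed-rank test at two-sided 0.05, as the single primary endpoint. State that it reflects about 80 min of humidification.
2. Make the area above the curve and the late image secondary, reported as estimates with intervals and not as grounds for claiming success.
3. Reconcile the 6-hour wording with the 4 h 10 min image, and state that this image is compared with the same image on the baseline day.
4. State which readout and time point the 7.7% SD describes. Item 7 ties it to none, so this is needed whichever primary is chosen. If it does not describe the chosen primary, re-justify the 6.8%. On the same paired-t basis the detectable change is 0.889 × SD: for example 8.9% for an assumed SD of 10%, or 10.7% for 12%.
5. If the data have already been examined, say so and report all readouts.

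The cost is a few sentences and no change to imaging procedures. The detectable change may need restating if the SD belongs to another readout. The real downside is that success can no longer be claimed on a secondary readout alone.

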Study of Humidified Air to Improve Mucociliary Clearance (MCC) in COPD:

NCT03935932

[name]., [name].
Pulmonary, Allergy and Critical Care Medicine
University of Pittsburgh

June 5, 2023

Statistical Analysis Plan:

We will plot normalized retention vs. time and compare the percentage of deposited material cleared at $t=90$ min and up to 6 hours on the intervention days. Areas above the curve 90 min clearance curve will also be compared. We will calculate the central deposition percentage of the Tc-SC aerosol to ensure that Tc-SC aerosol delivery was similar on both testing days.

Statistical comparisons will be made using paired non-parametric statistics to compare the baseline clearance day to the Airvo clearance day (Wilcoxon Signed Rank).
